3.3.4 Treatment compliance

Records of study medication used, dosages administered, and intervals between visits will be recorded during the study. Drug accountability will be noted and patients will be asked to return all unused study medication.

3.4 Visit schedule and assessments

3.4.1 Visit schedule

3.4.1.1 Screening Assessments

Written informed consent must be obtained and documented in the medical record before starting protocol therapy. After receiving a subject's agreement to participate in the study and verifying that the subject eligibility criteria, the study site will begin further pretreatment evaluation as follows:

- Clinical Evaluation: A complete history and neurological examination (including clinical assessment of Karnofsky Performance Status, Neurological function, neurologic exam score, Vital signs, Physical, and Mental Status) is to be done within 14 days of initial protocol treatment.
- Radiographic Evaluation: An MRI scan must be performed within 14 days prior to initial treatment on a dose of steroids that has been stable or decreasing for 5 days or more. MR spectroscopy are optional.
- Vital Signs: Height, pulse, blood pressure, respiration rate, temperature and weight. Blood pressure, pulse and respiration rate should be measured on patients.
- Laboratory Evaluation: Blood tests may be performed at the UCSF GCRC, at the UCSF Neuro-oncology clinic, or at a local laboratory. Pre-study laboratory tests must be obtained with 14 days prior to initial protocol treatment. Pre-study laboratory tests shall include:
 - CBC, platelets, differential, PT (INR)
 - Sodium, potassium, chloride, bicarbonate, calcium, fasting glucose, albumin, total protein, BUN, serum creatinine
 - T. bilirubin, AST, ALT, alkaline phosphatase, uric acid, phosphorus,
 - Fasting serum lipid profile (total cholesterol, triglycerides, HDL and LDL)
 - serum pregnancy test for women of childbearing potential (performed within 7 days of initial protocol treatment).

- Electrocardiogram (ECG): A standard 12 lead ECG is to be performed within 14 days of initial protocol treatment and significant findings must be recorded.
- Lung function: Pulse Oximetry and Chest X-ray must be performed within 14 days prior to initial protocol treatment

Hepatitis B/C testing: Patients will be tested for the following hepatitis serologic markers: HBsAg, HBs Ab, HBc Ab Total, HBc IgM Ab and HCV antibodies.

3.4.1.2. Assessments During Treatment

- Clinical Evaluation: Clinical assessments will be required every 2 months for the first 12 months, then every 3 months for the next 12 months. After 4 weeks of treatment, a toxicity check will be performed with a local MD or telephone. Whenever possible, all assessments at each scheduled time-point will be completed in a single clinic visit. Performance of a full clinical evaluation should take between 1-1.5 hours. Clinical assessments performed at required visits will include the following:

Karnofsky performance status (Appendix 17.2)

Neurological function / Neurologic exam (see below)

Physical Examination

Pulse Oximetry measurements

Neuro Exam: Neurologic status should be recorded at each patient visit according to the scale below (compared to baseline, defined as neurologic exam at time of screening).

+2	Definitely better
+1	Possibly better
0	Unchanged
-1	Possibly worse
-2	Definitely worse

Vital Signs: pulse, blood pressure, respiration rate, temperature and weight. Blood pressure, pulse and respiration rate should be measured on patients

- Radiographic Evaluation: An MRI will be required every 2 months for 12 months and every 3 months for the next 12 months. MR spectroscopy scans at these time points are optional. A research MRI/MRS scan maybe performed during Cycle 1 week 3. Required assessments will include measurement of bi-

directional diameters for patients who continue to have measurable disease. Uni-dimensional maximal diameter will also be recorded. MRI will be evaluated by Central Radiology review by both a neuro-oncology attending.

- Chest X-ray: A chest x-ray is required every 2 months for 12 months and every 3 months for the next 12 months.

Course Response: This will be recorded every time a patient has an imaging study.

+3	=	Disappearance of tumor (CR)
+2	=	Definitely better (PR)
+1	=	Possibly better
0	=	Unchanged
-1	=	Possibly worse
-2	=	Definitely worse (PD)
-3	=	Development of a new lesion (PD)

- Laboratory Evaluation: Laboratory tests except serum pregnancy tests shall be performed every 2 weeks during the first 2 months of treatment, and then monthly thereafter:
 - CBC, platelets, differential
 - Sodium, potassium, chloride, bicarbonate, calcium, fasting glucose, albumin, total protein, BUN, serum creatinine
 - T. Bilirubin, AST, ALT, alkaline phosphatase, uric acid, phosphorus
 - Fasting serum lipid profile (total cholesterol, triglycerides, HDL and LDL)
 - Serum pregnancy test: for women of childbearing potential every 2 months for 12 months and then every 3 months while on protocol therapy and 12 weeks after discontinuing protocol therapy.
 - Note the coadministration of RAD001 and oral anticoagulants is possible but should be subject to verification of coagulation (INR) once steady state is reached (after one week's treatment).
- Hepatitis B testing: Patients who test positive for hepatitis B antibodies without receiving prior vaccination will be monitored for HBsAg every 4 weeks.

- Medication Evaluation: All relevant information regarding drug doses, concomitant medications and doses, evaluable lesions with measurements, tumor response, laboratory examinations, and treatment-related toxicities shall be documented in the patient's medical record and flow sheets. Patients will maintain a treatment diary while on therapy. The Treatment Diary will be initiated on Day 1 of therapy and continue throughout treatment. Treatment

Diaries will be collected from the patient at 1 week, and then every 2 months for the first 12 months, then every 3 months until the patient discontinues therapy.

3.4.1.3 Follow-Up Assessments

- Protocol Completion Assessment:
 - After administration of RAD001 for two years, patients will be offered the opportunity to continue treatment. There is no limit to the course of treatment an individual patient may receive. However, the patient will continue to be evaluated at 3 month intervals while on RAD001 and a decision to discontinue treatment after 2 years of therapy will be made on clinical grounds.
 - All patients must be observed for safety for 30 days following the last dose of RAD001 prior to withdrawal from study. This defines study completion.
 - Physical examination and comprehensive neurologic examination and grading, vital signs including weight, Karnofsky Performance status, all laboratory values, and MRI of the brain must be repeated within 2 weeks of the last day of study only if these have not been evaluated within 14 days, inclusive, prior to the date of withdrawal from study.
- Long-term Follow-up:
 - Patients will be followed according to routine clinical practice after removal from protocol therapy or until death, whichever occurs first.
 - Patients removed from protocol therapy for unacceptable adverse events will be followed until resolution or stabilization of the adverse event.
 - All patients will be followed for PFS and OS while on protocol therapy and while still receiving subsequent routine clinical care. Patients off protocol therapy will continue to be followed for PFS and OS only.

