3.2.4 Monitoring of RAD001 suspected toxicities

Patients whose treatment is interrupted or permanently discontinued due to an adverse event or abnormal laboratory value suspected to be related to RAD001 must be followed at least weekly until the adverse event or abnormal laboratory resolves or returns to grade 1. If a patient requires a dose delay of > 28 days from the intended day of the next scheduled dose, then the patient must be discontinued from the study.

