Both asymptomatic radiological changes (grade 1) and symptomatic non-infectious pneumonitis (grade 2 = not interfering with activities of daily living or grade 3 = interfering with activities of daily living and oxygen indicated) have been noted in patients receiving RAD001 therapy. Non-infectious pneumonitis has been associated with RAD001 and other mTOR inhibitors (Atkins 2004). In order to monitor for asymptomatic (grade 1) pulmonary infiltrates, a chest X-ray is required if a CT scan of chest is not used for bi-monthly disease evaluations. Additional chest CT scans may be performed, when clinically necessary. If non-infectious pneumonitis develops, a consultation with a pulmonologist should be considered. If the patient develops grade 3 pneumonitis, treatment with RAD001 should be interrupted and the patient should be treated as medically indicated (short course corticosteroids, oxygen, etc). Management of non-infectious pneumonitis suspected to be associated with RAD001 and dose modifications instructions are provided in Table 3-2

Table 3-2 Management of non-infectious pneumonitis

Worst Grade Pneumonitis	Required Investigations	Management of Pneumonitis	RAD001 Dose Adjustment
Grade 1	CT scans with lung windows and pulmonary function testing including: spirometry, DLCO, and room air O₂ saturation at rest. Repeat chest x-ray/CT scan every 2 Cycles until return to baseline.	No specific therapy is required	Administer 100% of RAD001 dose.
Grade 2	CT scan with lung windows and pulmonary function testing including: spirometry, DLCO, and room air O₂ saturation at rest. Repeat each subsequent Cycle until return to baseline. Consider bronchoscopy *	Symptomatic only. Prescribe corticosteroids if cough is troublesome.	Reduce RAD001 dose until recovery to ≤ Grade 1. RAD001 may also be interrupted if symptoms are troublesome. Patients will be withdrawn from the study if they fail to recover to ≤ Grade 1 within 3 weeks.

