6.1.2. Endpoint Definitions and Sample Size

The following definitions will be used for statistical analysis:

- Response: Response is based on the best response. The best response is defined as the best objective status as measured by the sum of products of perpendicular diameters of all measurable lesions.
- Progression-free survival: Number of days from the day the patient was enrolled to the day the patient experiences an event of disease progression or recurrence or to the date of death if disease progression or recurrence is not reached. All events of disease progression or recurrence will be included, regardless of whether the event

occurred while the patient was still taking drug or had previously discontinued study drug. All events of death will be included for patients who had not experienced disease progression or recurrence. If the patient does not have an event of disease progression or recurrence nor as the patient died, the patient's data will be censored at the date of last contact with the patient.

- Overall survival: Number of days from the day the patient was enrolled until the date of death. If the patient is lost to follow-up, the patient's data will be censored at the date of last contact with the patient.

For this single-arm phase II trial, the primary endpoint will be 6-month progression-free survival (PFS-6). Patients will be analyzed based on intention to treat. The primary determination of treatment success will be based on the results for those patients who are shown to still be low-grade. The intent is to perform the primary analysis at the time the 6 month PFS is known for all patients.

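### Survival follow-up after stopping RAD001 is tied, ambiguously, to routine clinical care, with no duration or contact schedule, so deaths may be missed and overall survival overstated

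*Combined protocol and SAP*

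**What the plan says.** Three sentences under Long-term Follow-up in 3.4.1.3 bear on the point:

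- The general rule after removal from treatment: "Patients will be followed according to routine clinical practice after removal from protocol therapy or until death, whichever occurs first".
- The rule for the two time-to-event endpoints, with its routine-care condition: "All patients will be followed for PFS and OS while on protocol therapy and while still receiving subsequent routine clinical care".
- A further sentence, which restricts what is collected once treatment has stopped but does not repeat that condition: "Patients off protocol therapy will continue to be followed for PFS and OS only".

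Under Protocol Completion Assessment, the same section says: "All patients must be observed for safety for 30 days following the last dose of RAD001 prior to withdrawal from study". It treats that point as study completion. The last column of the assessment table (3.4.1.4) is 30 days after protocol therapy. It carries a toxicity check and no survival contact.

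The wording of treatment exits is mixed:

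- Section 3.2.4, on dose delays beyond 28 days: "then the patient must be discontinued from the study".
- Table 3-2, on grade 2 pneumonitis: "Patients will be withdrawn from the study if they fail to recover to ≤ Grade 1 within 3 weeks". The grade 3 row is worded alike, with a different time limit.
- The list after Table 3-2 puts adverse events and disease progression among the reasons for ending participation.
- Section 3.3.2 ends the study for the patient after a long toxicity delay.
- Section 3.3.3 has a patient who needs other anticancer drugs leave the study first.
- Table 3-1 only stops RAD001 for an interruption of 28 days or more, and 3.4.1.3 speaks of removal from protocol therapy for unacceptable adverse events.

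Section 6.1.2 plans an intention-to-treat analysis and says of OS: "If the patient is lost to follow-up, the patient's data will be censored at the date of last contact with the patient".

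**The concern.** OS is the second secondary objective and one of the outcomes for the p-Akt and PTEN analyses (fourth secondary objective; 6.1.4). Kaplan-Meier and Cox methods assume that a patient censored at a given time has the same outlook as those still followed. A rule that makes observation depend on remaining in routine care can break that assumption, because patients may leave care when they are deteriorating. There is no control arm with the same follow-up to offset a bias. The marker analyses are small: 6.1.4 expects about 20 positive low-grade and 15 positive high-grade cases, so there are few deaths to lose.

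**Working it through.** **1. The plan's own figures.** No figure is stated for OS, for loss to follow-up or for the length of survival follow-up. The only related design figure is the primary power in 6.1.2: 40 patients, 17% against 40%, one-sided alpha 0.05, power over 90%. By exact binomial, requiring at least 12 progression-free of 40 gives alpha 0.030 and power 0.929. The hazard ratio is ln(0.40)/ln(0.17) = 0.517, against the stated 0.52. Both reproduce, and neither depends on OS follow-up.

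**2. Reading the follow-up sentences together.** The sentence on routine care states a condition. The one after it limits what is collected off therapy; it neither repeats nor lifts the condition. The routine-practice-or-death sentence sets no schedule. Section 6.1.4 gives OS no cut-off of its own. The planned study duration in 6.1.3 is 20 + 6 = 26 months, with nothing added for survival. The text therefore does not settle who is contacted, how often, or until when.

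**3. Who is likely to leave.** The progression definition in 3.4.2.1 counts non-return because of death or decline as progression, unless clearly unrelated to the cancer. The authors thus foresaw patients who stop attending because they are worse, and PFS is protected against it. OS has no counterpart; such a patient, if contact is lost, is censored.

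**4. Size, under assumption.** Suppose a fraction f of deaths is censored just before death. The observed hazard is (1 − f) times the true hazard, so the Kaplan-Meier curve tends to S^(1−f).

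| True OS | f = 10% | f = 20% | f = 30% |
|---|---|---|---|
| 60% | 0.60^0.9 = 63.1% | 0.60^0.8 = 66.5% | 0.60^0.7 = 69.9% |
| 40% | 0.40^0.9 = 43.8% | 0.40^0.8 = 48.0% | 0.40^0.7 = 52.7% |

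The values of f and of true OS are assumptions; the documents give neither.

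**5. Dependence on who leaves.** A simulation (400,000 patients, exponential survival, administrative censoring at 36 to 60 months, assumed true median 24 months, so true 24-month OS 50%) gives these 24-month Kaplan-Meier estimates:

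| Pattern of loss | 5% | 10% | 20% | 30% |
|---|---|---|---|---|
| Contact ends 0–3 months before death (% of deaths) | 51.6 | 53.4 | 57.1 | 61.2 |
| Unrelated to prognosis (% of patients) | 50 | 50 | 50 | 50 |
| Longer survivors leave (% of patients) | 48.5 | 46.8 | 43.0 | 37.7 |

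The first row agrees with the formula: 0.50^0.9, 0.50^0.8 and 0.50^0.7 are 53.6, 57.4 and 61.6%. With an assumed median of 48 months (true 24-month OS 70.7%), the first pattern gives 72.0 to 78.4% and the third 70.0 to 64.6%.

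**6. Marker models.** Under the assumption in step 4, the same fraction f of events is lost. With the standard error of a log hazard ratio roughly proportional to 1/√events, it grows by 1/√(1−f): 1.05, 1.12 and 1.20 for f = 10, 20 and 30%.

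**The case against.** The strongest reply is that the section taken as a whole does not stop survival follow-up. The sentence right after the routine-care condition continues PFS and OS follow-up off therapy without repeating it, and another sentence mentions death as an end. This stands to the extent that the text is ambiguous. A reader might infer that follow-up lasts only while routine care continues; the section does not say that cleanly.

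A reader might also infer that a toxicity exit ends survival follow-up. No section says so. Table 3-1 and part of 3.4.1.3 speak only of drug or protocol therapy. Section 3.4.1.3 sets out long-term follow-up after defining study completion, so leaving the study may well mean leaving the treatment phase. The anticancer-agent rule in 3.3.3 is not a toxicity exit at all. Section 6.1.2 censors OS at last contact for loss to follow-up, not at drug stop. What remains is inconsistent wording that a site could apply either way.

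Nothing in the documents says that patients move to care elsewhere or that the site would not learn of their deaths. Telephone and local-physician contact is already used for the 4-week toxicity check in 3.4.1.2, so remote contact is feasible. But no section requires it for survival.

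**Conclusion.** The point holds as a weakness in the follow-up rule, not as a demonstrated bias. A reader might conclude that OS will be overstated; the documents do not support that as fact. Upward bias is the more plausible direction, because the protocol itself foresees non-return through deterioration and guards only PFS against it. Bias is nil if leaving care is unrelated to prognosis and reversed if longer survivors leave. If 10 to 30% of deaths were censored just before they occur, OS would read about 3 to 10 percentage points high at a true 60%, and about 4 to 13 points high at a true 40%. Across the patterns of loss in the working, a true 50% could read anywhere from 37.7 to 61.2%. OS has no target, power or decision rule, and the primary design is untouched, so this is a cheap improvement that protects a secondary endpoint.

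**What to change.** - **Section 3.4.1.3:** replace the routine-care condition for OS with ascertainment of vital status (alive or dead, with date) for every enrolled patient at a fixed interval, for example every 3 months, and at the analysis cut-off. This should apply wherever the patient is treated, by telephone, referring clinic or death records, until death or withdrawal of consent for follow-up.
- **Tables 3-1 and 3-2, the discontinuation list after Table 3-2, and Sections 3.2.4, 3.3.2, 3.3.3 and 3.4.1.3:** reconcile the wording so that stopping RAD001 or protocol therapy is distinct from leaving survival follow-up. No treatment-stopping rule needs to change for this purpose.
- **Section 6.1.2:** define an OS cut-off, censor patients known to be alive at that date, and report the reasons for any earlier censoring.

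The cost is a wording amendment and coordinator time: at most 60 patients × 4 contacts = 240 short contacts a year at a 3-month interval, with no added visits or procedures. The OS figure may turn out less favourable. The stated sample size and primary power do not change.

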3.4.1.4 Summary of Assessments

	Initial Screen	1-month Assessment	Assessments every 8 weeks (+3/-7days unless otherwise noted) for year 1 of therapy	Assessments every 12 weeks (+3/-7days unless otherwise noted) after first year of therapy	30 days after completing protocol therapy
Procedure:					
Clinical Evaluation	X		X	X	

Vital Signs	X		X	X	
Neurologic Exam	X		X	X	
Toxicity Check	X	X	X	X	X
Chest X-Ray	X		X Q 8 weeks (+/-7days)	X Q 12 weeks (+/-7days)	
Pulse Oximetry	X		X	X	
ECG	X				
Laboratory/ Diagnostic Tests:					
Serum pregnancy for women of child-bearing potential	X		X Q 8 weeks (+/- 3 days)	X Q 12 weeks (+/- 3 days)	
CBC with diff and platelets					
Chemistries					
Liver function tests					
Fasting cholesterol / triglycerides					
MRI of the brain	X		X	X	
Hepatitis B/C testing HBsAg, HBs Ab, HBc Ab Total, HBc IgM Ab and HCV antibodies	X		Patients who test positive for HBV antibodies without prior vaccination will be tested for HbsAg every 4 weeks (+/- 7 days) for re-activation		
Translational Research:					
Archival tumor tissue	X				
Study Drug:					
RAD001 starting dose:			10mg		

3.4.2 Efficacy assessments

3.4.2.1 Response Definitions

Standard anatomic MRI in conjunction with clinical evaluation such as neurologic status and corticosteroid use, remains the key determinant of response to therapy and the evaluation of tumor recurrence for low grade glioma. Increase in contrast enhancement, worsening cerebral edema, and mass effect are traits of malignant transformation. Acquiring tissue samples to confirm tumor upgrade, although considered the “gold standard” for determining the presence of viable tumor, can result in both false positives and negatives that relate to sampling error. Evaluating response in low-grade glioma by radiographic imaging is an accepted means of determining response and is the standard by which NIH grant-funded brain tumor consortiums operate.

One of the secondary endpoints will be response rate, based on the best response achieved (see below for definition of best response). In order to ensure comparability of data from this trial with data from earlier trials, this trial will retain the traditional evaluation definition as the primary way to define response. Response will be determined by the bi-dimensional diameters. However, RECIST criteria will be collected and used for secondary evaluation.

Definitions of Response

Measurable Disease: Bidimensionally measurable lesions with clearly defined margins by MRI scan. A measurable lesion must be 1 mm or larger in longest diameter.

Evaluable Disease: Unidimensionally measurable lesions, masses with margins not clearly defined.

Objective Status, To Be Recorded at Each Evaluation: If there are too many lesions to measure at each evaluation, choose the largest two to be followed before a patient is entered on study. The remaining lesions will be considered evaluable for the purpose of objective status determination. Unless progression is observed, objective status can only be determined when ALL measurable and evaluable sites and lesions are assessed.

Complete Response (CR): Complete disappearance of all measurable and evaluable disease. No new lesions. No evidence of non-evaluable disease. All measurable, evaluable and non-evaluable lesions and sites must be assessed using the same techniques as baseline. Patients must be on minimal or no steroids.

Partial Response (PR): Greater than or equal to 50% decrease under baseline in the sum of products of perpendicular diameters of all measurable lesions. No progression of evaluable disease. No new lesions. All measurable and evaluable lesions and sites must be assessed using the same techniques as baseline. Responders must be on the same or decreasing doses of dexamethasone.

Partial Response, Non-Measurable (PRNM): Not applicable.

Stable / No Response (NR) / No Change (NC): Does not qualify for CR, PR, or progression. The designation of Stable/No Response requires a minimum of 8 weeks duration. All measurable and evaluable sites must be assessed using the same techniques as baseline.

Progression: 25% increase in the sum of products of all measurable lesions over smallest sum observed (over baseline if no decrease) using the same techniques as baseline, OR clear worsening of any evaluable disease, OR appearance of any new lesion/site, OR failure to return for evaluation due to death or deteriorating condition (unless clearly unrelated to this cancer).

Unknown: Progression has not been documented and one or more measurable or evaluable sites have not been assessed.

Best Response: This will be calculated from the sequence of objective statuses.

For patients with all disease sites assessed every evaluation period, the best response will be defined as the best objective status as measured according to the previously noted definitions. Best response is unknown if all objective status determinations before progression are unknown.

Neurological Exam: Although not used for determining response, it is useful to evaluate improvement in the neurologic exam that should coincide with objective measurement of tumor size.

+2 Definitely better
+1 Possibly better
0 Unchanged
-1 Possibly worse
-2 Definitely worse
(compared to baseline)

Time to Death: From date of registration to date of death due to any cause.

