3.2.2.3 Radiographic Inclusion Criteria

- Patients must have evidence for tumor recurrence or progression by MRI as determined by radiographic review of images by an attending neuro-oncologist or neuro-radiologist at UCSF
- If the steroid dose is increased between the date of the MRI and registration on the trial, a new baseline MRI is required. This MRI must be performed after ≥ 5 days on a stable or decreasing dose of steroids
- An MRI must be used throughout the period of protocol treatment for tumor measurement
- Patients must have evaluable disease

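### The 1 mm minimum for a measurable lesion, with no absolute minimum change, lets sub-millimetre differences count as PFS-6 progression when very small lesions make up the whole sum

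*Combined protocol and SAP*

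**What the plan says.** All the relevant definitions are in the combined protocol and SAP.

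- **Measurable disease (3.4.2.1).** "Bidimensionally measurable lesions with clearly defined margins by MRI scan", followed by "A measurable lesion must be 1 mm or larger in longest diameter". No minimum is set for the perpendicular diameter, and there is no slice-thickness condition.
- **Scale (3.4.2.1).** "Response will be determined by the bi-dimensional diameters". RECIST data are collected for secondary evaluation only.
- **Progression (3.4.2.1).** "25% increase in the sum of products of all measurable lesions over smallest sum observed", or baseline if there was no decrease. Separate limbs cover clear worsening of evaluable disease, new lesions, and failure to return because of death or deterioration. There is no absolute minimum increase and no confirmatory scan.
- **Eligibility (3.2.2.3).** "Patients must have evaluable disease". Eligibility sets no larger minimum size.
- **Endpoint (6.1.2).** PFS-6 is primary. "All events of disease progression or recurrence will be included, regardless of whether the event" falls before or after the drug is stopped.
- **Scans and review.** Section 3.4.1.2 requires MRI every 2 months in year 1, about three on-treatment scans by 6 months, with central review. Section 3.4.2.3 adds review of objective responses and adjudication of discrepant measurements by a second neuro-oncologist. It refers to criteria in a section 9.1, which is not in the text supplied.

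**The concern.** A relative rule works only when the percentage change it asks for is larger than reading error. The change needed in millimetres shrinks with the lesion, so the size floor is what protects the rule. At 1 mm the floor gives almost no protection. Because the comparator is the smallest sum seen so far, a larger lesion that shrinks on treatment can also enter the vulnerable range, and one low reading makes the next ordinary reading look like growth.

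The consequence falls on the primary endpoint: a false progression turns a PFS-6 success into a failure. Under section 3.3.1 drug is given until progression, so a false call would also end study treatment. The 50% shrinkage rule for partial response has the same weakness, but objective response is a secondary endpoint.

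**Working it through.** **1. The plan's own figures.** Section 6.1.2 gives 17% against 40%, N = 40, one-sided alpha 0.05, power over 90% and a hazard ratio of 0.52.
- Hazard ratio: ln(0.40)/ln(0.17) = 0.517.
- Exact binomial: requiring at least 12 of 40 successes gives alpha 0.030 and power 0.929. Requiring 11 gives alpha 0.066, so 12 is the smallest valid cut-off.

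Both stated figures reproduce. The plan attaches no calculation to the 1 mm rule.

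**2. Change needed to reach 25%.** If both diameters grow by the same factor f, then f² = 1.25, so f = 1.118. The increase per diameter is 0.118 x d.

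| Starting diameter | Increase in each diameter | Increase if only one diameter changes |
|---|---|---|
| 1 mm | 0.12 mm | 0.25 mm |
| 5 mm | 0.59 mm | 1.25 mm |
| 10 mm | 1.18 mm | 2.5 mm |
| 20 mm | 2.36 mm | 5.0 mm |

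Check at 1 mm: 1.12 x 1.12 = 1.254, a rise of 25.4%.

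**3. Dependence on the rest of the sum.** If a 1 x 1 mm lesion grows to 1.12 x 1.12 mm beside an unchanged 20 x 20 mm lesion, the sum goes from 401 to 401.254 mm², a rise of 0.06%. The problem exists only where small lesions make up essentially the whole sum.

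**4. False progression in a stable lesion.** The setting is one square lesion with no true change and independent normal error on each diameter (400,000 simulated patients). The error SD of 0.5 to 1.0 mm is assumed. At 1 mm an unrestricted normal model gives 42–46% per comparison, but it produces at least one zero or negative diameter in 9% (SD 0.5) to 50% (SD 1.0) of comparisons. The 1 mm row is therefore restricted to positive baseline diameters with a longest reading of at least 1 mm, and follow-up readings are floored at zero.

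| True diameter | One comparison | Three scans, smallest-sum rule |
|---|---|---|
| 1 mm | 26–30% | about 87–88% |
| 3 mm | 26–38% | 71–87% |
| 5 mm | 13–29% | 47–77% |
| 10 mm | 1–13% | 7–47% |

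At 20 mm a single comparison gives 0 to 1.3%. The three-scan column takes no account of reader judgement or adjudication.

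**5. What it could cost.** False progressions only remove successes. If 10% of true successes were lost, the 40% rate would become 36% and power at 12 of 40 would fall from 0.93 to 0.83. If 20% were lost, the rate would be 32% and power 0.66. These loss rates are illustrations, not estimates. To lose 10% through stable lesions of about 5 mm, the share of would-be successes with such a lesion as their whole sum would have to be 0.10/0.77 = 13% to 0.10/0.47 = 21%. The documents do not give that share.

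**The case against.** The best defence is that the dangerous case may be rare.

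- Some patients enter after biopsy only, so their tumour is largely in place. All need MRI evidence of recurrence, and section 1.1.3.4 describes these tumours as diffuse.
- A lesion without clear margins is already evaluable rather than measurable, so the 25% rule does not apply to it.
- When there are too many lesions to measure, the two largest are followed.
- Readers have a scale that separates possible from definite worsening, and central review and adjudication stand behind them.

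Most of this stands. A reader might infer that small residues are the norm after subtotal resection, and so that PFS-6 is badly contaminated. The documents do not show that: they give no lesion sizes and no reading error. The power losses in the last step of the working must not be read as forecasts.

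The defence does not remove the defect. Review and adjudication settle what the measurement is; they do not supply a minimum change or a confirmatory scan. A reader who follows the text must call a sub-millimetre rise progression when the sum is small enough. That 1 mm may be a unit slip is a reason to correct it, since nothing in the supplied text does so.

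The objection also holds against the remedy in part. At an error SD of 1.0 mm, a 10 mm floor still leaves 13% false rises per comparison, and the documents offer no support for 10 mm in particular.

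**Conclusion.** The point holds as a defect in a threshold on which the primary endpoint relies, and it should be corrected. The arithmetic (0.12 mm per diameter at 1 x 1 mm) rests on the documents alone. The false-rise probabilities rest on an assumed reading error, independent errors and a single stable lesion. The effect on this trial's PFS-6 cannot be sized, because the share of patients whose sum is dominated by small lesions is unknown.

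The direction is clear. A reader might infer that noisy measurement could produce a falsely positive trial. For false progressions the opposite is true: they lower PFS-6, work against the drug and cost power without inflating type I error. False shrinkage could raise the response rate, but that is secondary.

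**What to change.** 1. Confirm whether 1 mm in section 3.4.2.1 is a unit or typing error.
2. Replace it with a minimum diameter at which a 25% change in the product exceeds the site's own MRI reading error. As an example, 10 mm would require about 1.2 mm in each diameter, ten times the present requirement.
3. If the site's reading error is near 1 mm, add an absolute minimum increase to the 25% rule, because a 10 mm floor alone would not be enough.
4. Extend the definition of evaluable disease to lesions below the floor, so that they are judged under the existing limbs for clear worsening and new lesions. Eligibility need not change, since it already asks only for evaluable disease.

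The cost is a short amendment. Some patients move from measurable to evaluable, and their progression calls become more subjective. Partial response is defined on measurable lesions, and its non-measurable counterpart is marked not applicable, so the ORR denominator shrinks slightly. The analysis section should say how those patients are counted.
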